8.1 HANDLING OF WITHDRAWALS

All participants prematurely discontinued from the study, regardless of cause will be encouraged and given the opportunity to be seen for a final evaluation. The reason(s) for withdrawal will be recorded in the CRF by the study coordinator and/or investigator.

10.0 PROTOCOL DEVIATIONS

Protocol Deviations will be recorded by the study coordinator.

11.0 ADVERSE EVENTS

An adverse experience (AE) is any experience that suggests a significant hazard, contraindication, side effect, or precaution. With respect to human clinical experience, a serious adverse experience includes any untoward event that is fatal or life-threatening, is permanently disabling, requires or prolongs hospitalization, is a congenital anomaly, cancer, result of an overdose, or requires intervention to prevent permanent damage. In

the event of a serious adverse experience, the principal investigator or study coordinator must be contacted immediately by telephone. In the event that the principal investigator or study coordinator cannot be directly reached, a message must be left by voice mail within 24 hours of the incident.

All adverse events will be recorded although a distinction will be drawn between reactions normally experienced in conjunction with conventional periodontal therapy extractions and experiences not usually encountered. Unanticipated or possible related adverse events will be evaluated by open questioning throughout the trial. Examples of adverse events that may warrant subject removal from study participation include: infection, loss of primary stabilization, excessive inflammation, swelling, bleeding or pain. The onset, duration, treatment, and outcome of all such unanticipated adverse experiences must be recorded on the appropriate case report forms and reported within 7 business days to the Biomedical IRB. All anticipated and unrelated adverse experiences will be recorded on the appropriate case report forms.

The following definitions of severity should be used in the evaluation of AEs:

- Mild*: an AE that is easily tolerated and does not interfere with daily activities.
- Moderate*: an AE that is sufficiently discomforting so as to interfere with daily activities or receive interventional treatment.
- Severe*: an AE that prevents normal everyday activity.

The following definitions of relationship to implant surgery should be used in assessing the suspected causality of an AE:

- Probably Related*: there is a direct cause and effect relationship between the AE and the surgical procedure
- Possibly Related*: a direct cause and effect relationship between the surgical procedure and the AE has not been demonstrated, but is likely, possible, or cannot be ruled out, even if improbable
- Unlikely Related*: a direct cause and effect relationship between the surgical procedure and the AE has not been demonstrated, and, from the available data, indicate that a relationship probably does not exist, but cannot be definitely ruled out
- Remote*: a direct cause and effect relationship between the surgical procedure and the AE has not been demonstrated, and, the event appears to have been caused by something other than the study device
- Not related*: a direct cause and effect relationship between the AE and a source other than the surgical procedure has been demonstrated and documented

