3.2 RANDOMIZATION

Qualified subjects will be assigned randomly into one of two groups: 12 subjects into the xenograft + 3D-collagen group (Test) and 12 subjects into the xenograft + collagen dressing group (Control).

The study coordinator will place 24 identically sized slips of paper, 12 reading "Test" and 12 reading "Control", into a sealed envelope. The study coordinator will select one sealed envelope for each qualified subject, and record the randomization results and staple the slip of paper into the subject study folder.

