5.3 VISIT 2 (DAY 0): BASELINE

The baseline visit should be completed within 2 weeks after visit 1 (Screening). The surgeon will extract the hopeless tooth in the following fashion. He/she will make facial and lingual intrasulcular incisions with a 15-C scalpel only at the tooth requiring extraction. A periosteal elevator will then be used at the mesial and distal aspects of the tooth to sever subcrestal periodontal attachment fibers and expand the periodontal ligament space. If needed to allow periosteal elevator insertion or facilitate removal of a root tip, a fine long diamond bur (e.g. 859-010;

Brasseler, Savannah, Ga, USA) may be used to remove bone along the side of the tooth. An elevator will be used to mobilize the tooth and then forceps will be used to deliver the tooth. Finally, the socket will be curetted to remove all granulosomatous tissue and irrigated with sterile isotonic saline solution.

1. Extraction treated with xenograft bone substitute + collagen dressing:

The debrided socket from the control group will receive Geistlich Bio-Oss® Collagen (250mg) or the necessary amount to successfully fill the extraction socket. The bone substitute material will be rehydrated with subject's blood or sterile saline solution. A collagen dressing (HeliPlug®) will be used to cover the grafted extraction socket and sutured with resorbable suturing material (5-0 Vicryl – Ethicon, Inc., Somerville, NJ) to stabilize the wound.

2. Extraction treated with xenograft bone substitute + 3D-collagen matrix:

The debrided socket from the test group will receive Geistlich Bio-Oss® Collagen (250mg) or the necessary amount to successfully fill the extraction socket. The bone substitute material will be rehydrated with subject's blood or sterile saline solution. A 3D-collagen matrix (Mucograft Seal®) will be used to cover the grafted extraction socket and sutured with non-resorbable (6-0 Prolene – Ethicon, Inc., Somerville, NJ) and resorbable (5-0 Vicryl – Ethicon, Inc., Somerville, NJ) suturing material to stabilize the collagen matrix over the extraction socket.

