5.8 VISIT 7 (MONTH 6 +/- 7 DAYS)

Visit 7 may occur within 6 months of visit 2 (+/-7days). The following procedures will be performed:

- Study personnel will record changes in medical history and concomitant medications since the previous visit and ask continuance criteria questions.
- Participant vital signs (blood pressure and pulse) will be recorded.
- Standardized cone beam computed tomography (CBCT) will be taken for implant surgical planning.
- 3Shape Trios scanning will be completed for later volumetric analysis.
- Adverse events will be monitored and recorded as necessary

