7.0 STATISTICAL ANALYSIS

Descriptive statistics (means and standard deviations for continuous variables and frequencies for categorical variables) will be produced for vital signs, demographic characteristics, medical history and clinical variables, both overall, and for each of the two groups of study participants. Summaries of clinical variables will be presented at baseline and at study exit. Adverse events (including onset, duration, treatment, outcome and suspected causality) and reasons for withdrawals will be listed and summarized.

A power analysis was performed using a statistical power calculator (SAS Power Procedure, Cary, NC). This study will have a sample size of 24 subjects, 12 in each of the two groups. We will have at least 90% power (with a Type I error rate of 5%) to detect a difference of 2.5mm in the horizontal ridge width measured at 3mm below the most coronal aspect of the crest, assuming a standard deviation of 1.6mm, as determined by a previous study (Jung, Philipp et al. 2013). This power calculation takes into account the estimated 10% of subjects drop out. A “p” value of less than 0.05 will be considered statistically significant.

For soft tissue analysis, the primary outcome was the within-participant difference between the linear and volume changes at the test and control groups. These differences were measured in each participant prior to surgery, as well as 3 and 6 months after surgery, leading to a series of three longitudinal differences for each participant. For each group, the differences at all three time points were analyzed simultaneously using a linear mixed model (LMM), in which the actual linear and volume measures were modeled as a function of time (categorical), treatment group, and the interaction of time and treatment, while accounting for the repeated measures on each participant with a random participant effect. Given that both time and treatment are categorical, our approach was a generalized version of repeated measures ANOVA, as our LMM allowed for differing variability in linear and volume measures at each time point. Within each LMM, we also tested for a difference between the two treatment groups with respect to the overall time pattern in linear and volume measures. Due to the exploratory nature of the analysis, no Bonferroni correction for multiple testing was applied. Statistical significance was defined as a p -value < 0.05 .

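### The adverse-event causality scale has three different anchors and none names the randomised covering, so relatedness ratings for the first six months are unreliable.

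*Combined protocol and SAP*

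**What the plan says.** Section 11.0 contains the only causality scale, and its lead-in reads "The following definitions of relationship to implant surgery should be used in assessing the suspected causality of an AE". Five categories follow. *Probably related* means that "there is a direct cause and effect relationship between the AE and the surgical procedure". *Remote* ends with the condition that "the event appears to have been caused by something other than the study device". *Not related* applies when "a direct cause and effect relationship between the AE and a source other than the surgical procedure has been demonstrated and documented". No definition names the extraction, the graft or either collagen covering, and *study device* is not defined anywhere.

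The randomised contrast (section 3.2) is the covering over a common xenograft. It is placed on Day 0 (section 5.3, Visit 2), where the test matrix "will be used to cover the grafted extraction socket and sutured with non-resorbable" and resorbable material; the control dressing gets resorbable sutures only. The month-6 visit is Visit 7 (section 5.8), and implant surgery follows at Visit 8 (section 5.9) in both arms.

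Adverse events are recorded from Visit 3 to Visit 9 (sections 5.4 to 5.10). Section 7.0 plans that "Adverse events (including onset, duration, treatment, outcome and suspected causality) and reasons for withdrawals will be listed and summarized". That sentence does not say the summary is by arm.

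**The concern.** A causality rating should address the exposure under study. Here the lead-in points to a later procedure that both arms undergo, while the exposure that differs between arms is applied on Day 0. The harms most likely to differ, such as wound breakdown, graft infection or a reaction to the matrix, would arise during socket healing, before the procedure named in the lead-in has taken place.

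The rating is also used. It enters the section 7.0 summary. In section 11.0, unanticipated events go to the IRB within 7 business days, while anticipated and unrelated ones are recorded on the case report form. A wrong or inconsistent rating could therefore affect reporting as well as tables.

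**Working it through.** The plan gives no figure on this point, so the main check sets the definitions against the visit schedule.

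**1. One event, three anchors.** Take a wound reaction at week 2 that is shown to be caused by the covering.

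| Anchor used by the rater | Where it appears | Consequence |
|---|---|---|
| Implant surgery | Lead-in | Another source has been demonstrated: *Not related* |
| Surgical procedure, read as the Visit 2 operation | All five categories | Direct cause: *Probably related* |
| Study device, read as the covering | *Remote* only | *Remote* is excluded |
| Study device, read as the implant | *Remote* only | The device clause of *Remote* is met |

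Two raters can both follow the text and score the same event at opposite ends of the scale.

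**2. How much follow-up is affected.** Inputs: Visit 7 at 6 months, taken as 26 weeks; Visit 8 within 2 weeks of Visit 7, ±7 days; Visit 9 two weeks later. Section 5.10 counts Visit 9 from itself, so I assume Visit 8 is meant.

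- Visit 8 at 26 + 2 = 28 weeks and Visit 9 at 28 + 2 = 30 weeks. Share before implant surgery: 28/30 = 93%.
- Visit 8 immediately after Visit 7: 26/28 = 93%. Visit 8 three weeks after Visit 7: 29/31 = 94%.

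This is a share of follow-up time. The documents give no expected event rates, so it is not a share of events.

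**3. What a comparison by arm can do without a rating.** Inputs: 12 per arm (sections 3.2 and 7.0). With no events in one arm and x in the other, the two-sided Fisher p-value is 2 × C(12,x) / C(24,x).

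- x = 4: 2 × 495 / 10,626 = 0.093.
- x = 5: 2 × 792 / 42,504 = 0.037.
- With 0/12 events, the one-sided 95% upper bound on the rate is 1 − 0.05^(1/12) = 22%.

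The comparison is valid, but only a large imbalance (0 versus 5 of 12) reaches p < 0.05. Event-level judgement therefore carries much of the safety information in this trial.

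**The case against.** The strongest reply is that this is loose drafting with little effect.

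- **The categories can be read to include socket surgery.** All five refer to the surgical procedure, and only the lead-in says implant surgery. Section 9.0 speaks of surgical procedures in the plural for graft and implant alike, and section 11.0 itself distinguishes the usual reactions to extraction. This stands: the scale does not unambiguously exclude the Visit 2 procedure. It does not remove the problem, because the lead-in is the instruction to the rater and it says otherwise.
- **Early harms can still be assessed.** A reader might infer that harms of the two coverings in months 0 to 6 cannot be attributed at all. The documents do not support that. All adverse events are to be recorded, with onset, from Visit 3 on, and allocation is random, so early events can be compared by arm whatever their rating.
- **Early events are not *Remote* or *Not related* by default.** A reader might infer that every event before Visit 8 would be rated so. *Not related* requires another source to be demonstrated and documented, and *Remote* turns on a device that may well be the covering. The supportable statement is that such events could be rated so on a literal reading.
- **No event drops out of the tables.** A reader might infer that a table of related events would miss early harms. Section 7.0 plans no table restricted to related events; causality is one listed attribute.
- **A rating against the Visit 2 procedure cannot isolate the covering.** This is correct. Extraction and graft are common to both arms, and only the comparison by arm separates the covering (with its suturing) from them. The fix therefore needs both the rating and the by-arm table.

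**Conclusion.** Wrong as written. The scale has three anchors that do not agree, and none names the randomised covering. Followed literally, its lead-in can give *Not related* to an event caused by the randomised treatment. Event-level relatedness is therefore unreliable for about 93% of planned follow-up time, assuming a 26-week month-6 visit and Visit 9 two weeks after Visit 8.

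The damage is limited to that rating and whatever uses it. The recording of events and their onset, the randomised comparison of early events, and the radiographic and soft-tissue outcomes are not affected. The documents show inconsistent wording and give no sign of a deliberate decision to leave socket-phase harms out.

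**What to change.** 1. In section 11.0, reconcile the three anchors. Rate each adverse event twice with the existing five categories: (a) against the Visit 2 extraction, graft and covering procedure, and (b) against the Visit 8 implant surgery.
2. Replace *study device* with the named randomised covering. In rating (b), make the matching clause of *Remote* refer to the implant procedure.
3. In section 7.0, state that adverse events with onset before Visit 8, with rating (a), are tabulated by arm. Include every such event whatever its rating, because section 3.1 masks only the volumetric assessments and raters may know the allocation.

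The cost is one extra CRF field and some protocol wording. No treatment, visit or sample size changes.

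### The adverse event causality levels in section 11.0 overlap, so counts of Possibly Related, Unlikely Related and Remote cannot be reliably separated

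*Combined protocol and SAP*

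**What the plan says.** Section 11.0 makes one scale the basis for coding: "The following definitions of relationship to implant surgery should be used in assessing the suspected causality of an AE". It has five levels:

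- *Probably Related*: "there is a direct cause and effect relationship between the AE and the surgical procedure".
- *Possibly Related*: a direct link "has not been demonstrated, but is likely, possible, or cannot be ruled out, even if improbable".
- *Unlikely Related*: a direct link is again not demonstrated, and the available data "indicate that a relationship probably does not exist, but cannot be definitely ruled out".
- *Remote*: a direct link is not demonstrated, and "the event appears to have been caused by something other than the study device".
- *Not related*: some other cause has been shown and put on record.

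The section gives no rule for choosing when an event fits more than one level. The scale feeds a planned output: the sentence in section 7.0 that begins "Adverse events (including onset, duration, treatment, outcome and suspected causality" says that these events will be listed and summarised. It does not say how the five levels will be grouped or tabulated.

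**The concern.** A causality scale should give each event one code. Here the definition of *Possibly Related* runs from likely down to improbable, so it takes in territory that the levels on either side appear meant to cover. Two careful raters could code the same event differently and both be following the protocol.

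What is at stake is the breakdown of adverse events by suspected causality. If the boundary between the middle levels is a matter of rater choice, a difference between arms in the number of *Possibly Related* events could reflect coding habit and not the treatments. The risk grows if the rater knows the arm. Section 3.1 states masking only for the volumetric assessments, and no masked causality rater is described.

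**Working it through.** No arithmetic applies. The documents state no figure for the scale, and the point depends on no sample size, effect size or error rate. The check is to compare the five definitions condition by condition.

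| Level | Status of the link to the procedure | Further condition | Also meets *Possibly*? |
|---|---|---|---|
| *Probably* | exists | none | no |
| *Possibly* | not demonstrated | likely, or possible, or not excluded however improbable | – |
| *Unlikely* | not demonstrated | data point against a link, but it is not excluded | yes, always |
| *Remote* | not demonstrated | event appears to have another cause | yes, unless the link is fully excluded |
| *Not related* | another source demonstrated and documented | none | no |

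1. **Shared condition.** *Possibly*, *Unlikely* and *Remote* all start from a link that has not been demonstrated, so that condition cannot tell them apart.
2. ***Unlikely* against *Possibly*.** A link that probably does not exist is an improbable one. *Unlikely* also requires that the link cannot be excluded. Those two features are what the closing clause of *Possibly* admits, so every *Unlikely* event satisfies *Possibly*. This is containment, not a shared border. The two definitions are not identical, because *Unlikely* also asks that the data point against a link.
3. ***Remote* against *Possibly*.** An apparent other cause does not by itself exclude a link to the procedure. Unless the link is fully excluded, a *Remote* event also satisfies *Possibly*.
4. ***Remote* against *Unlikely*.** An event that appears to have another cause will often be one where the data suggest no link. These two levels are not clearly separated from each other either.
5. **Top of the scale.** *Probably* is worded as an existing relationship. A link that is likely but not demonstrated fails it and is named under *Possibly*.
6. **End levels.** *Probably* and *Not related* do not share the undemonstrated-link condition, so they stay separable from the middle three.

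Result: three of the five levels overlap, and *Possibly* also holds the likely links that a reader would expect to find under *Probably*.

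The reference procedure also varies. The lead-in to the scale names implant surgery, four levels refer to the surgical procedure, and *Remote* switches to the study device. Yet the randomised covering materials are placed at extraction (section 5.3, Visit 2), about six months before the implant (section 3.0).

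**The case against.** The strongest defence is that a sensible rater picks the most specific level that fits, so an event that meets both *Possibly* and *Unlikely* is coded *Unlikely*. That would settle the nested pair, but the documents do not state the rule. It would also leave likely links under *Possibly* and would not settle *Remote* against *Unlikely*, which are not clearly nested.

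Four stronger readings are tempting and are not supported:

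- **That the causality summary cannot be read at all.** The end levels are distinct, the middle levels can be pooled, and section 7.0 also plans a listing with onset, duration, treatment and outcome. With 24 subjects that listing can be reviewed event by event. No test, threshold or stopping rule is tied to the causality code.
- **That the code decides which events are followed up.** Section 11.0 says "Unanticipated or possible related adverse events will be evaluated by open questioning throughout the trial". This does not use the defined level name and reads most naturally as the way events are elicited, before any code is given. Adverse events are monitored at every visit from 3 to 9, all are to be recorded, and reporting to the review board turns on whether an event is unanticipated.
- **That the rater is known to be unmasked.** It is plausible: the coverings and sutures differ by arm (section 5.3, Visit 2), the allocation slip is stapled into the subject folder (section 3.2), and the study number identifies the group (section 4.4). But the documents do not say who assigns causality, and for healing problems section 9.0 brings in a second therapist from outside the investigation. Knowledge of the arm is therefore an assumption.
- **That recoding one event shifts a safety result by 1/12 = 8.3 percentage points.** That is the weight of one subject in any binary variable with 12 per arm. It does not measure this defect. Moving an event between two levels leaves the arm's adverse event total unchanged, events are not subjects, and the denominator may exceed 12 because section 4.4 replaces non-completers.

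**Conclusion.** The point holds as a defect of definition. On the plain wording, *Unlikely Related* lies inside *Possibly Related*, *Remote* meets *Possibly* unless the link is excluded, and likely links are placed one level lower than the label *Probably* suggests. The separate counts for *Possibly*, *Unlikely* and *Remote* will not be reliable.

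The size is limited to the split among three of the five levels of one descriptive safety output. The documents give no expected number of adverse events, so the number that could be coded two ways cannot be estimated. The conclusion rests on a literal reading of the definitions and on the absence of a precedence rule. Bias between arms would need the further assumption that the rater knows the arm. This is a minor point, worth correcting because it costs so little.

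**What to change.** Reword the levels so that each event has one code:

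- *Possibly Related*: delete the word *likely* and the closing clause that admits improbable links which cannot be excluded. State that what remains means a reasonably possible link with other causes equally plausible, because anything not excluded is possible in the bare sense.
- *Probably Related*: define as a link that is likely, and say that a demonstrated link also belongs here.
- *Unlikely Related*: keep for a link that is improbable but not excluded.
- *Remote*: merge with *Unlikely*, or state what separates them. If it is left as it stands, the overlap with *Unlikely* remains.

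Alternatively, keep the levels and state in section 7.0, in advance, that they will be pooled as related / not related by one rule applied to both arms. The cut must not run between the overlapping levels. Counting any link that has not been excluded as related would meet that condition.

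In the same edit, reconcile the reference procedure. The lead-in (implant surgery), the levels (surgical procedure), *Remote* (study device) and the step at which the randomised materials are placed (extraction) should agree, so that each event is judged against a named exposure.

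The cost is rewording the definitions and the case report form key. It needs no extra data, visits or staff.
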